13.2. First screening interview (a three-step process carried out in a single interview)

- Participants contact the study themselves by phone (text, phone, or email contact) or are approached by an NYU study staff member in an indoor or outdoor venue. Participants may contact the study themselves using an online contact form linked to a QR code in ads and flyers.
- **Consent:** Potential participants will provide verbal informed consent for the screening interview following an IRB-approved script
- **Screening interview:** After consent is obtained, they will participate in a brief (< 15 minute) structured screening interview using the Computer-Assisted Personal Interview (CAPI) format in REDCap to determine eligibility.
- **Part 1** will comprise basic demographic information including whether the participant resides in New York City. If participants meet the eligibility criteria in Part 1, they will continue to Part 2.
- Part 1 will ask:
 - how participant heard about the study
 - how interview will be conducted (virtually or in person)
 - date of birth
 - age
 - can engage in study activities in English or Spanish
 - resides in NYC (by self-report and confirmed by eliciting a New York City mailing address.)
- Part 2 will ask the remaining eligibility criteria, except for vaccination.
- Part 3 will ask about vaccination and check documentary evidence of vaccination.
- **Part 3 includes eliciting documentary evidence of vaccination:** There are three ways to document COVID vaccination status: 1) by accessing or allowing us to access the “My Vaccine Record” through NYC Health (as described in more detail below), 2) the participants may provide documentary evidence of COVID-19 vaccination such as the CDC vaccine card or MyChart record. They can provide a photograph of their vaccine card to the study; or 3) self-report. This information will be entered into REDCap (dates and type of vaccine for each dose of vaccine).

- Those who do not meet all eligibility criteria in Parts 1 and 2 will not be asked to complete My Vaccine Record, since that is time consuming. But, they will be asked to provide their vaccination card or vaccination information by self-report.
- **Locator:** Those found eligible and who did not complete the contact form will provide some locator information, to facilitate future contact and scheduling. Those who completed the contact form may not need to provide additional locator information at this stage.
- Screening can take place in recruitment venues, the NYU study field site, or virtually.
- During the informed consent process (for screening and enrollment), participants will be informed that their participation is voluntary and that their declining to enroll in the study will not affect any services or resources they might otherwise receive. They will be given opportunities to ask questions about the study. They can delay providing informed consent until another time and date.
- Note that we will not compensate participants for screening.
- Regarding COVID-19 precautions, NYU staff and other investigators and participants will follow NYU guidelines including completing the daily screener app, wearing face coverings, and social distancing, as appropriate. NYU staff and other investigators will be vaccinated for COVID-19 and their COVID-19 vaccination card will be uploaded to the NYU health portal and approved.

13.4. Enrollment, intervention, and follow-up phase

13.4.1. Visit 1 (Enrollment)

- Enrollment will take place at the NYU field site or virtually.
- Participants will provide electronic signed informed consent in REDCap for enrollment, complete a more detailed locator form to facilitate longitudinal FU, and participate in a structured BL interview programmed in REDCap.
- **Consent:** Those who participate virtually will provide verbal consent and a copy of the consent form will be mailed or emailed to them. Those who participate in-person can provide signed informed consent using the eConsent feature. A copy of the consent form will be provided to them.
- **Locator:** Then, more detailed locator information will be obtained to facilitate future contact.
- **Baseline:** They will then complete the baseline interview using CAPI and ACASI in REDCap. The baseline survey will last < 60 minutes.
- **Randomization:** They will be randomly assigned to an intervention condition using a randomization table in REDCap.
- **Core session:** Then, they have the opportunity to engage in the core session, or to schedule it for the next 1-2 weeks. Typically, the baseline and core session will be carried out on the same day.
- Compensation and funds for local round-trip transportation provided
- **A thank you card** will be sent to the participant by mail and electronically after enrollment (text will be IRB-approved)
- The project will send **birthday cards** to participants by mail and electronically (text will be IRB-approved)
- The project will send regular **holiday cards** to participants by mail and electronically (text will be IRB-approved)

13.4.2. Intervention components

- Intervention components will generally be administered after the baseline interview, and within the 1-2 weeks after enrollment. Components are brief or carried out mainly independently, thus Components A-D can be implemented in a single session.
- Intervention components can be carried out in person at the NYU field site or virtually over the phone or Voice over Internet Protocol such as Zoom.
- **During the core session, participants will be reminded to collect and retain documentary evidence of any COVID testing for the follow-up assessments.**

13.4.3. Time 2 and Time 3 assessment (6-weeks and 12-weeks post BL)

- Takes place in-person in a private office at the NYU field site or virtually
- Within 2-4 weeks prior to the assessment, the participant will be contacted and reminded to provide documentary evidence of COVID-19 testing, if any, and to attend the follow-up interview even if not tested for COVID-19. Participants can provide evidence of as many tests as they like.
- Participants will also be asked to provide documentary evidence of COVID-19 vaccination if they have it (e.g., the CDC vaccination card).
- Follow-up (FU) assessments will be carried out 6- and 12-weeks post-BL in ACASI or CAPI in the REDCap platform.
- The FU interviews will last approximately 35-45 minutes. The 6- and 12-week FUs will assess the period since the last interview.
- The locator form may be confirmed or updated at each phone or in-person contact with participants
- In-between FUs, participants may contact the study to update contact information.

13.4.4. Qualitative in-depth interview (subset of participants; N~50)

- Participants will be purposively sampled for the qualitative in-depth interviews for maximum variability on the following criteria: age, sex, language (English or Spanish), race/ethnicity, type of occupation, whether engaged in assigned components or not, and whether was tested for COVID-19 or not (N=50).

- We will explore participants' experiences with and perspectives on the intervention components (including acceptability) and on barriers to and facilitators of COVID-19 testing, as well as barriers to and facilitators of vaccination, and on the relationship between COVID-19 testing and vaccination.
- The qualitative interview will follow a semi-structured guide that has main questions linked to the conceptual model and probes. We will also attend to emergent topics.
- Interviews will be audio-recorded and transcribed.
- Qualitative and quantitative results will be integrated, as described below.
- The qualitative sample size was determined following procedures outlined by Malterud¹¹⁹ called information power. Greater sample heterogeneity and a cross-case analysis strategy as we propose here call for larger samples; $N=50$ is a larger sample size.
- Takes place in-person at the field site or virtually (phone or Voice over Internet Protocol such as Zoom)
- 60-90 minutes
- Compensation and funds for local round-trip transportation provided

13.5. Acuity

We will use the Acuity program for participant scheduling. In Acuity, participants can be sent a link with available slots and can schedule an appointment. They can enter their name and contact information and Acuity will send reminder texts or emails.

The Acuity program maintains participant confidentiality. It is a password protected program (on a password protected computer) and participants see only available slots, not the names of other participants.

Participants can schedule their own visits and we can use Acuity to schedule appointments for them.

13.6. Preventing repeat enrollments

Staff members will check and flag data as possibly fraudulent (i.e., the same person[s] attempting to complete the screening interview and/or enroll in the study multiple times) using an algorithm based on a combination of geolocation data, survey data, and personal information (Ballard et al., 2019). Data that will be reviewed by staff for potential fraud include geolocation outside the study area based on IP or mailing addresses, multiple entries from the same IP or mailing address address, phone numbers that are invalid or belong to a business or organization, phone numbers that match previous entries, unusual email addresses (e.g., containing alternating letters and numbers), email address that matches previous entries, date of birth/name that match previous entries, duration of the survey was less than 5 minutes. Staff members will contact participants suspected of fraud to inform them that their entry was flagged and to request they contact staff members to verify their entry to receive compensation. Participants who cannot be verified will be determined fraudulent and not included in the final dataset.

The informed consent forms state that participants should not take the survey more than once, and if this occurs, incentives will not be received more than once.

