15.5. Statistical methods

15.5.1. Quantitative data analysis

Intent-to-treat analysis will be our primary analytic approach and exploratory analyses will examine complier average effects of intervention components^{124,125}. Approaches to missing data will include full information maximum likelihood estimation¹²⁶ and multiple imputation¹²⁷. In sensitivity analysis, missing data will be treated as failure to achieve the desired outcome. If data are missing not at random (MNAR), we will employ sensitivity analysis, using selection¹²⁸ or pattern mixture^{129,130} models.

Aim 1: Identify which of four components or interactions between components contribute meaningfully to improvement in the primary outcome, COVID-19 testing with documentary evidence, and from these results, optimize a multicomponent intervention.

The primary outcome for Aim 1 is COVID-19 testing with documentary evidence by the final follow-up point (12-weeks post-baseline). Logistic regression will be used to estimate effects of components on the odds of COVID-19 testing. Intervention components will be effect-coded to estimate main effects, two-way, three-way, and four-way interactions of all four components (see **Equation 1**). The coefficient for an effect-coded main effect term (e.g., b_1), multiplied by two and exponentiated, will estimate the effect of the component (e.g., Component A) on the odds of testing. Similarly, the coefficient for an effect-coded interaction term, multiplied by two and exponentiated, will estimate interaction effects between or among components on the odds of testing. Similar logistic regression analyses will estimate effects of components on secondary outcomes.

Equation 1

Intervention optimization. Based on main and interactive effects estimated in Aim 1, we will use a decision-making process to select the most effective combination of component levels, eliminating ineffective or poorly performing components. The decision-making process will be led by Drs. [name], [name], [name], [name], and [name] and using procedures outlined in Collins⁴⁸. To identify

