16.19.1. Timing of compensation

For all activities, compensation will be provided immediately after the activity is completed or as soon as possible after the activity is completed.

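### The fraud rule in section 13.6 has no cut-off at randomisation, so it can remove unique randomised participants and compromise the intent-to-treat analysis

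*Combined protocol and SAP*

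**What the plan says.** Section 13.6 has staff flag possible fraud, meaning the same person "attempting to complete the screening interview and/or enroll in the study multiple times". The flags draw on location, repeated IP or mailing address, phone, email, name and date of birth, and a survey lasting under five minutes. Staff tell flagged people that their entry was flagged and ask them "to request they contact staff members to verify their entry to receive compensation". The consequence of failing is: "Participants who cannot be verified will be determined fraudulent and not included in the final dataset".

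Four other sections bear on the timing and the analysis:

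- Section 13.2, on screening: "Note that we will not compensate participants for screening".
- Section 13.4.1 lists Visit 1 in the order consent, locator form, baseline interview, randomisation, core session, compensation. On randomisation it says: "They will be randomly assigned to an intervention condition using a randomization table in REDCap". Enrolment may be virtual.
- Section 16.19.1: "For all activities, compensation will be provided immediately after the activity is completed or as soon as possible after the activity is completed". In section 16.19 the first paid interview is the baseline.
- Section 15.5.1: "Intent-to-treat analysis will be our primary analytic approach". That section does not define the intent-to-treat set and does not mention the section 13.6 exclusion.

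**The concern.** Intent-to-treat protects the comparison because everyone assigned a condition is analysed in it. Removing a confirmed second entry by the same person does no harm to this if the decision rests on pre-randomisation information. Removing a unique person because a query went unanswered is different. Answering is then behaviour after assignment, and it may be related both to condition and to whether the person would have supplied evidence of a test.

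The planned missing-data methods cannot repair such a removal. Likelihood methods, multiple imputation and the sensitivity analysis that counts missing as not tested all work on records still in the dataset. A deleted record enters none of them.

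**Working it through.** **1. Can the rule act after randomisation?** Set the sections side by side. The scope in 13.6 covers enrolling as well as screening. The query concerns an entry on which compensation depends. Screening earns none (13.2), and at Visit 1 compensation comes after randomisation (13.4.1). A query raised around the first payment, plus the time for the person to call back, can end after assignment. Nothing in 13.6 excludes this and nothing requires it.

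**2. Does it reach people who are not duplicates?** The criterion is being unverifiable, and verification requires the person to contact staff. A unique person who does not call back can therefore meet it. Flags such as a shared IP or mailing address, or an unusual email address, do not themselves prove duplication.

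**3. The plan's sample size (section 15.1).** Inputs: alpha .05 (taken as two-sided), 80% power, 20% versus 33.3% (odds ratio 2.0), equal allocation.

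N = 2(1.960 + 0.842)² × [1/(.20 × .80) + 1/(.333 × .667)] / (ln 2)² = 2 × 7.849 × (6.25 + 4.50) / 0.4805 = 351.2, which gives 352 (16 × 22). Then 352/0.80 = 440, rounded up to 16 × 28 = 448. The stated figures reproduce, and this point does not dispute them.

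**4. Effect on power.** Assume removals come on top of 20% attrition and are unrelated to outcome. With none removed, 448 × 0.80 = 358.4, or 179.2 per component level, and power is 81.7% (pooled two-proportion test, 20% versus 33.3%). Removing 2%, 5% or 10% of those randomised gives 80.9%, 79.7% or 77.5%. The loss is small.

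**5. Possible bias.** The removal rates are assumed; the documents give none. Take 224 per level, no other attrition, and a true rate of 20% at both levels. Remove a fraction g of non-testers only. The odds of testing at a level become .20/[.80(1 − g)], so with no true effect the observed odds ratio is (1 − g₁)/(1 − g₂). Type I error uses the Wald test of the log odds ratio.

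| Non-testers removed, level 1 vs level 2 | Observed rates | Odds ratio (2 vs 1) | Type I error |
|---|---|---|---|
| 5% vs 5% | 20.8% vs 20.8% | 1.00 | 5.0% |
| 5% vs 10% | 20.8% vs 21.7% | 1.06 | 5.6% |
| 0% vs 10% | 20.0% vs 21.7% | 1.11 | 7.3% |
| 0% vs 15% | 20.0% vs 22.7% | 1.18 | 10.5% |
| 0% vs 20% | 20.0% vs 23.8% | 1.25 | 15.4% |

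Bias favours the level that loses more non-testers. Only the most extreme row exceeds the 1.2 threshold in section 15.5.1, and a component must also reach p < .05 to be screened in. Type I error is therefore the more useful column.

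**The case against.** The strongest reply is that 13.6 is an entry control. Its title concerns repeat enrolments, its definition of fraud concerns repeat screening or enrolling, and most flags use information available before randomisation. The phrase about compensation may be a forward-looking warning to someone flagged at screening. Randomised participants have also completed a detailed locator form naming at least three contacts (section 16.1.3), so few should be unreachable. Keeping unverifiable records risks analysing duplicates or ineligible people.

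Much of this stands, and it limits what can be claimed. Four stronger readings are tempting but unsupported:

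- *The plan breaks intent-to-treat.* Removal after randomisation is allowed by silence, not instructed.
- *Non-responders are excluded by rule.* The text says unverifiable. Non-response matters only because verification depends on the person making contact.
- *Component B's texts would make removal differ by condition.* If queries arise at baseline payment, they largely precede the six weeks of messages. That mechanism needs late queries, which 13.6 does not describe.
- *The under-five-minute flag would catch people at follow-up.* The stated definition of fraud covers screening and enrolment only.

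The reply does not remove the gap. If the rule is meant only for entry, the section does not say so, and its link to compensation makes the later reading a natural one.

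**Conclusion.** The point holds as a gap in the rule. As written, section 13.6 can remove unique randomised participants, without blinding to condition and without requiring proof of duplication, and so can compromise the stated intent-to-treat analysis. The documents do not show that this will happen, or that it would differ by condition.

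The size is unknown. In the illustration it runs from no bias under equal removal to an odds ratio of 1.25 under an extreme 0% versus 20% removal. Those figures rest on assumed removal rates, on every removed person being a non-tester, and on a 20% true rate. The sample size of 448 is unaffected. This is a cheap improvement to the plan, not a major flaw.

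**What to change.** In section 13.6:

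- Require fraud checks to be completed before REDCap assigns a condition.
- After randomisation, allow exclusion only for confirmed duplicates or false identities, judged on pre-randomisation data by staff blind to condition and outcome.

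In section 15.5.1:

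- Define the intent-to-treat set as all unique individuals assigned a condition.
- Keep other unverified randomised participants in that set under the planned missing-data methods.
- Add a sensitivity analysis that excludes them.
- Report all post-randomisation exclusions by condition.

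The cost is a change of wording, a short hold on randomising flagged entries only, and the possible retention of a few unverifiable records in the primary set. The added sensitivity analysis shows whether those records matter.

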13.7. Implementation manual

The COVID-19 pandemic requires a rapid public health response but the rapid scale-up of effective interventions in community settings lags substantially¹¹⁶. The proposed study will draw on implementation science principles to support timely implementation of the optimized intervention if found effective. We will develop an implementation strategy manual, detailing requirements and recommendations for implementation in NMIC and similar community-based settings. To create the manual, we will conduct CAB meetings with stakeholders at NMIC including staff and clients who are BLH-FEW. Guided by the Consolidated Framework for Implementation Research (CFIR)¹¹⁷, the meetings will explore potential barriers and facilitators to implementation of the optimized intervention in community-based settings. The CFIR is one of the most widely utilized frameworks in implementation science¹¹⁷. It is a meta-theoretical framework that provides a standardized list of constructs found to be implementation determinants across five major domains¹¹⁷. We will probe for barriers and facilitators organized by CFIR domains: outer setting factors (i.e., funding, policies), inner setting (i.e., leadership, organizational readiness), the intervention (i.e., complexity), the people involved (i.e., self-efficacy) and the implementation process (i.e., planning). After each CAB meeting, we will map group suggestions onto existing implementation strategies¹¹⁸. [name], a study Senior Advisor and expert on implementation science, will play a leadership role in this effort along with our partners at NMIC. Further, integrated qualitative and quantitative results from the factorial experiment will be presented to the CAB and included in the evaluation of implementation factors. Ultimately, the findings will form the basis of a manual providing tailored guidance related to the organizational context to support rapid adoption of the optimized intervention after the study is concluded.

13.8. Subject completion/withdrawal

Participants may withdraw from the study at any time without prejudice to their care. They may also be discontinued from the study at the discretion of the Investigator if they violate the study plan, due to adverse events, or to protect the subject or staff for reasons of safety or for administrative reasons.

14. Study Evaluations and Measurements

14.1. Screening assessment domains

We will assess the following by self-report:

1. Age
2. Able to conduct activities in English or Spanish
3. African American or Black and/or Latino or Hispanic race/ethnicity
4. Residence in the NYC
5. In the past month, was employed as a frontline worker in an essential occupation listed in this protocol
6. Has a phone that can be used for study participation and can receive TMs (in the event the participant is assigned to Component B)
7. Has not been fully vaccinated for COVID-19 (we will ask to see vaccine certificates if available but this is not required and those who have not received any dose of a vaccine will not have a certificate)

8. Has not been tested for COVID-19 in the past six months
9. If previously diagnosed with COVID-19, has not been symptomatic in the past two weeks or 90 days has passed since treatment with monoclonal antibodies or convalescent plasma
10. Has not been educated/interviewed as a peer for Component C
11. Willing to engage in a core session and be randomly assigned to receive 1-4 components
12. Not a Community Advisory Board member
13. Willing to follow NYU's COVID-19 guidelines (e.g., complete daily screener, facial coverings, social distancing)
14. Willing to provide locator information

14.1.1. Domains in the assessment battery (BL and FU), Table 4

We will use the Common Data Elements developed by the RADx-UP group for the majority of domains described in Table 4.

Table 4. Description of the measures in the assessment battery (RADx-UP Common Data Elements will be used)

Moderating influences	
Screening CDE	Identity, Age, race/ethnicity, sex assigned at birth, preferred language (CDE), ZIP code of residence, essential worker (Are you considered an essential worker? An essential worker is someone who was required to go to work even when stay at home orders were in place.)
Socio-demographics, background factors	sexual orientation, gender identity, immigration status, racism and discrimination experiences, ¹⁰³
	Health status - CDE
	Highest level of education – CDE
	Housing Employment and Insurance - CDEs
	Effects of COVID - CDEs
	Family income – CDE
	Past COVID-19 testing - CDE
	Medical History - CDE
Other CDEs	
Alcohol and tobacco	Alcohol and tobacco
	Work PPE and Distancing
Individual/attitudinal influences	
Knowledge	8-item true-false questionnaire on aspects of COVID-19 ¹⁰⁴
Perceived susceptibility to, severity of COVID-19	Wong perceived susceptibility to (three items), and perceived severity of COVID-19 infection (three items) scales ¹⁰⁵
Perceived benefits of COVID-19 testing	Guidry 4-item Perceived Benefits of COVID testing ¹⁰⁶ ; $\alpha = 0.82$
Distrust and fear of COVID-19 testing	10-items assessed on a 5-point Likert-type scale drawn from existing reliable scales ¹⁰⁶⁻¹⁰⁸
Counter-narratives (conspiracy theories)	6-items assessed on a 5-point Likert-type scale drawn from existing reliable scales (e.g., I could be a guinea pig for a test with unknown consequences). ^{109,110}
Cognitive biases	Measurement of BE biases ⁴²
Behavioral Intentions	Various testing scenarios assessed with 3 items (e.g., I intend to get a COVID-19 test regularly) on a 6-item Likert scale ¹⁰⁶
Motivation/readiness	Importance of COVID testing and confidence in ability to get serial screening and tested as needed on a 1-100 scale. ¹¹¹
Social influences	
Perceived social norms	Adapting Latkin we will assess social norms using four items: injunctive (e.g., My co-workers encourage me to get a COVID test); descriptive (e.g., What percent of your co-workers do you think have gotten a COVID test) ¹¹² . $\alpha = 0.77$.
Altruism & collective responsibility	Three items on testing as an altruistic act (e.g., My getting tested helps my community reduce the spread of COVID) ¹⁰⁸
Structural influences	
Structural barriers to COVID-19 testing	Perceived barriers including poor access related to insufficient local sites, lack of paid sick leave, lack of childcare, language barriers ¹¹³
PRIMARY OUTCOME	
COVID-19 testing	COVID testing behavior (see protocol for definition)
SECONDARY OUTCOMES	
COVID-19 testing	Confirmatory and/or re-testing, contact tracing (by participant), self-isolation, health care, unintended consequences of testing
Vaccination	Testing behavior - CDE
	Vaccine Acceptance - CDE
	Attitudes toward COVID-19 vaccination ¹⁰⁶⁻¹⁰⁸ , receipt of vaccination doses
Intervention process domains	
Intervention acceptability	Client Satisfaction Questionnaire (YCSQ) –17 items; reliable and valid measure ¹¹⁴
Intervention social harms	Assessment of project-related social harms experienced in social and occupational domains.
Feasibility/Intervention dose	
Intervention dose	Number of assigned components attended, if assigned: number of peers educated, navigation contacts completed and their characteristics/content

